#### **5.3.2. Main Analytical Approach**

Estimand strategy: While on treatment.

Analysis set: Safety (see [Table 3](#)).

Analysis methodology: Descriptive only.

[figure not shown]
Intercurrent events and missing data: AE data will no longer be collected on subjects who discontinue early from the study except as required to resolve an ongoing AE. See [Section 6.6.3 \(Appendix 6\)](#) for details on handling of missing AE information.

See [Section 5.6.2](#) for details on AE summaries and listings.

### **5.4. Exploratory Endpoints Analysis**

#### **5.4.1. Definition of Endpoints**

#### **5.4.2. Main Analytical Approach**

## **5.5. Other Safety Analyses**

### **5.5.1. Extent of Exposure**

Study drug exposure will be summarized as total number of doses and dose duration (days), separately for INDV-2000 (Safety Population) and buprenorphine (Run-In Safety Population). For INDV-2000, exposure will be summarized for study days 3-9 (with buprenorphine), study days 10-13 (without buprenorphine) and study days 3-13. For buprenorphine, exposure will be summarized for run-in, study days 1-2 (without INDV-2000), study days 3-9 (with INDV-2000), and study days 1-9.

### **5.5.2. Adverse Events**

A TEAE is an AE that started at or after first administration of IMP. A run-in AE is an AE that started at or after first administration of study drug during the run-in period. AEs will be assigned to study treatments based on start dates and times of treatments and start dates and times of AEs.

AEs will be coded to a System Organ Class (SOC) and Preferred Term (PT) using Medical Dictionary for Regulatory Activities (MedDRA). Additional details of the coding process, including the current version of the dictionary, are described in the Data Management Plan. All AEs will be listed for individual subjects. Listings will include SOC, PT, and reported term; treatment; onset date and time, end date, and duration; run-in status, treatment-emergence, severity, toxicity grade (though not required for Part III of the study), seriousness and seriousness criteria; relationship to study drug; action taken with IMP; action taken with SUBOXONE SL film; whether concomitant treatment was given; outcome; and whether the AE resulted in study discontinuation. Duration (days) is calculated as the AE end date – the AE onset date +1; for ongoing AEs, the date of end of study participation will be used as the end date. Duration will be missing if either the start or end date is partially or completely missing. SAEs, TEAEs leading to IMP discontinuation or interruption, AEs leading to SUBOXONE SL film discontinuation or interruption, and fatal AEs will be listed separately.

The incidence and number of all TEAEs, TESAEs, study drug-related TEAEs and TESAEs, severe TEAEs, TEAEs leading to IMP discontinuation or interruption, and fatal TEAEs will be presented in an overall summary table.

TEAEs, TESAEs, study drug-related TEAEs and TESAEs, and run-in AEs will be summarized by MedDRA SOC and PT, each in descending order of frequency among all subjects within study part (then alphabetically in case of ties). TEAEs will also be

summarized by maximum severity within SOC and PT. If an AE is reported more than once by a subject within a SOC and/or PT, the maximum reported level of severity will be used at each level of summation in the severity summary table.

Incidence and number of TEAEs will also be summarized by PT only (ie, not SOC), sorted by descending frequency among all subjects (within study part).

Non-treatment-emergent, non-run-in AEs are defined as AEs that started either before first administration of study drug or after the run-in period but before first administration of IMP and will be summarized for the run-in safety population.

See Section [6.6.3 \(Appendix 6\)](#) for details on handling of missing AE information.

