9.6 Prior and Concomitant Therapies

Therapies and medications will be collected from screening until the EOS visit or the ET visit, at the time points listed Section 22.1, Appendix 1, Section 22.2, Appendix 2 and Section 22.3, Appendix 3. Any concomitant medications (including herbal preparations) taken during the study will be recorded in the source documents and in the eCRF. Any changes in concomitant therapy and medications during the study will be documented, including cessation of therapy and medication, initiation of therapy and medication and dose changes.

Prior therapies and medications are considered any medication ended prior to first dose of study drug. Therapies and medications are considered concomitant if taken after dosing with IMP.

For Part III, therapies and medications taken after study drug but prior to IMP are considered run-in therapies and medications.

Any changes to concomitant therapies and medications that are not listed as permitted concomitant therapies and medications must be discussed with the study Medical Monitor.

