10.1.1 Time Period for Collecting Adverse Events

Adverse event monitoring and reporting will begin after subjects sign the ICF, continue throughout the study and include EOS/ET/Follow-up. Subjects will be monitored by the study site staff for untoward effects and will be released from the study after the last procedure is completed and confirmed that the subject has no residual untoward effects from the study drug that may affect safety. Treatment-emergent AEs will be defined as events observed after starting administration of INDV-2000 or placebo. For Part III, run-in AEs will be defined as events observed after starting SUBOXONE SL film and before starting INDV-2000.

Surgical procedures, planned before enrolment of the subject in the study, are not considered AEs if the condition was known before study inclusion. In this case the medical condition is to be reported in the subject's medical history.

Any clinically significant symptoms will be reported as AEs. All AEs and corresponding treatment will be recorded in the eCRFs and a summary of all safety data will be presented in the final Clinical Study Report (CSR). Any ongoing AEs will be appropriately followed up until resolution or 14 days after EOS/ET. If findings are noted in the 90 day post last dosing day safety follow up call for male participants, these will be recorded as Adverse Events and followed until completion of required assessments. The study site personnel will make every effort to contact the subject as outlined in Section 6.6.2, after which the outcome of the AE will be considered ongoing and the subject will be noted in source as lost to follow-up.

If a subject experiences the onset of an SAE within 5 days following study completion and in the opinion of the Investigator, that SAE is associated with the study drug, it will be followed and reported as described in Section 11.2.

Confidential Page 56 of 108

If an SAE occurs that is deemed related to study drug, a PK sample will be taken as soon as possible after the event is reported. If possible, an additional sample should be collected when the SAE has been resolved.

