### **5.1.5. Definitions**

IMP: INDV-2000 or placebo (placebo not applicable in Part III)

---

Study Drug: INDV-2000, SUBOXONE SL film, or placebo (placebo not applicable in Part III).

Screening Period: Informed consent to Day -7 Clinic Check-In.

Run-In Period: Day -7 to Day -1 Run-In Assessment

End-of-Study (EOS): Early termination or completion of last scheduled visit.

Enrolled Subject: Met Day -1 run-in assessment criteria.

Study Day 1: day of first dose of study drug administration after the run-in period.

Study day:

- Study day = date of assessment – date of Study Day 1 + 1, for assessments on or after Study Day 1
- Study day = date of assessment – date of Study Day 1, for assessments before Study Day 1

Study time: time of assessment – time of first study drug administered in the clinical unit.

Duration:

- Duration in days = end date – start date + 1
- Duration in minutes = end time – start time. Durations will be adjusted for Daylight Saving Time, where applicable.

Baseline observation: for a given parameter for a given subject, the last observed value, including unscheduled and repeated assessments, before the first dose of IMP or planned first dose of IMP if IMP was not administered.

Run-in baseline observation: for a given parameter for a given subject, the last observed value, including unscheduled and repeated assessments, before the first dose of study drug during the run-in period.

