### **5.6.3. Prior and Concomitant Medications and Therapies**

Medications and therapies will be collected from screening through EOS and will be coded using Anatomical Therapeutic Chemical (ATC) classification codes via the World Health Organization Drug Dictionary (WHO-DD). Additional details of the coding process, including the current version of the dictionary, are described in the Data Management Plan. Prior medications and therapies will be medications/therapies that ended before first administration of study drug or were taken by subjects who did not take study drug. Therapies and medications that were started or were ongoing during run-in will be considered run-in therapies and medications. Therapies and medications that were started or were ongoing post run-in will be considered concomitant therapies and medications. A therapy or medication can be both run-in and concomitant. Therapies/medications will be assigned to study treatments based on start dates and times of treatments and start and end dates and times of therapies/medications.

Prior concomitant medications and therapies will be summarized for all subjects. Run-in medications and therapies will be summarized for the run-in safety population. Concomitant medications and therapies will be summarized for the safety population. The summary of incidence (number and percentage of subjects reporting the medication/therapy at least once) will be sorted alphabetically by therapeutic class (ATC level 2) and standardized medication/therapy name.

See Section [6.6.4 \(Appendix 6\)](#) for details on handling missing information on medications and therapies.

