### **Missing AE Start Date/Time Information**

Note: partial times will not be recorded in the CRF.

An AE will be considered a run-in AE for the Run-In Safety Population under the following conditions:

- Missing start year, month, day, time and it can be deduced from non-missing components of AE end date that the AE ended before first IMP.
- Missing start month, day, time if start year is equal to or after year of first study drug during run-in and it can be deduced from non-missing components of AE end date that AE ended before first IMP.
- Missing start day and time if start year is after year of first study drug during run-in or if start year is equal to year of first study drug during run-in and month is equal to or after month of first study drug during run-in and it can be deduced from non-missing components of AE end date that AE ended before first IMP.
- Missing start time if start date is on or after date of first study drug during run-in and it can be deduced from non-missing components of AE end date that AE ended before first IMP.

An AE will be considered treatment emergent for the Safety Population under the following conditions:

- Missing start year, month, day, time unless it can be deduced from non-missing components of AE end date that the AE ended before first IMP.
- Missing start month, day, time if start year is equal to or after year of first IMP, unless it can be deduced from non-missing components of AE end date that AE ended before first IMP.
- Missing start day and time if start year is after year of first IMP or if start year is equal to year of first IMP and month is equal to or after month of first IMP, unless it can be deduced from non-missing components of AE end date that AE ended before first IMP.
- Missing start time if start date is on or after date of first IMP.

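### Part III run-in ends at first INDV-2000 in the protocol but at Day -1 in most of the SAP, and SAP 5.5.2 gives no end for the last treatment period

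*SAP*

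**What the plan says.** **End of run-in, adverse events.** Protocol 10.1.1 says "For Part III, run-in AEs will be defined as events observed after starting SUBOXONE SL film and before starting INDV-2000". In the Part III schedule that means up to Day 3. SAP 5.1.5 sets "Run-In Period: Day -7 to Day -1 Run-In Assessment". SAP 5.5.2 says "A run-in AE is an AE that started at or after first administration of study drug during the run-in period". That sentence alone could be read as open-ended, but the section goes on to define a third class, neither run-in nor treatment-emergent. This class holds events that began before any study drug "or after the run-in period but before first administration of IMP", so the SAP's run-in class stops at Day -1.

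SAP 6.6.5 classifies events with incomplete start information and applies no Day -1 cut. An event is run-in under "Missing start time if start date is on or after date of first study drug during run-in and it can be deduced from" the end date that it was over before first IMP.

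**End of run-in, medications.** Under protocol 9.6, "therapies and medications taken after study drug but prior to IMP are considered run-in therapies and medications", and a medication becomes concomitant only after IMP dosing. SAP 5.6.3 differs: "Therapies and medications that were started or were ongoing post run-in will be considered concomitant therapies and medications". The same section adds "Concomitant medications and therapies will be summarized for the safety population", and that population requires at least one IMP dose.

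**Differences from the protocol.** SAP 1 says these are identified in Appendix 2. The visible rows list only the added Screened and Enrolled populations.

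**End of treatment.** SAP 5.5.2 assigns an event to a treatment from the start of the treatment and the start of the event. SAP 5.6.3 uses treatment starts with medication start and end. Neither mentions a treatment end. The columns in SAP 5.1.3 are SUBOXONE, INDV-2000+SUBOXONE, INDV-2000 and All Subjects. Protocol 14.7.1 follows the primary endpoint to final follow-up, and protocol 4.1 lets subjects begin other OUD treatment once the Day 14 assessments are done.

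**The concern.** On the first point, the same event or medication is classified differently depending on the section the programmer follows. For adverse events the SAP also disagrees with itself: whether a clock time was recorded can change the class of an event whose date is known. The outputs at stake are the run-in AE table that protocol 14.9.1 asks for, the table of events that are neither run-in nor treatment-emergent, and the run-in and concomitant medication tables.

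On the second point, the Part III objective is safety of INDV-2000 both alone and with SUBOXONE, and the by-treatment AE columns carry that distinction. With no stated end, an event after the last dose stays with the last treatment started. For a subject who follows the schedule that is INDV-2000 alone, so events after dosing, possibly on another OUD treatment, would read as events on INDV-2000 alone. OUD medication begun after Day 14 would be attributed in the same way.

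**Working it through.** There is no plan figure to reproduce: Part III is descriptive and has no power calculation. The check applies each rule as written to example events and then counts days.

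**Inputs.** Run-in SUBOXONE on Days -6 to -1 (protocol Appendix 3). SUBOXONE alone on Days 1-2, both drugs on Days 3-9, INDV-2000 alone on Days 10-13 (SAP 1.2). First IMP is therefore Day 3. EOS is Day 21 ± 3 days (protocol Appendix 3).

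**Step 1: example events.**

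| AE start to end | Protocol 10.1.1 | SAP 5.5.2, start time recorded | SAP 6.6.5, start time missing |
|---|---|---|---|
| Day -3 to Day -2 | run-in | run-in | run-in |
| Day 1 to Day 2 | run-in | neither class | run-in |
| Day 2 to Day 5 | run-in | neither class | no rule assigns it |
| Day -3 to Day 5 | run-in | run-in | no rule assigns it |
| Day 3 to Day 4 | TEAE | TEAE | TEAE |

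There are two landmarks, first IMP and Day -1. SAP 6.6.5 shares the protocol's landmark but tests when the event ended, whereas the protocol tests when it began. This is why the rows ending on Day 5 have no rule when the start time is missing.

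**Step 2: medications.** A medication taken only on Days 1-2 is run-in under protocol 9.6 and concomitant under SAP 5.6.3. If the subject then receives no INDV-2000, SAP 5.6.3 gives it no summary:

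- It is not prior, because study drug had been taken.
- It is not run-in, because it started after run-in.
- It is not in the concomitant table, because the subject is outside the Safety Population.

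**Step 3: days in dispute.** SUBOXONE-alone dosing days = 6 (run-in) + 2 (Days 1-2) = 8. Share outside the SAP run-in class but inside the protocol's = 2/8 = 25%.

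**Step 4: the open last period.** Days from Day 10 to EOS = EOS day - 10 + 1. Of these, 4 are dosing days (Days 10-13). Days after the last dosing day = total - 4. Days after Day 14 = EOS day - 14.

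| EOS day | Total from Day 10 | After last dosing day | After Day 14 |
|---|---|---|---|
| 18 | 9 | 5 (55.6%) | 4 (44.4%) |
| 21 | 12 | 8 (66.7%) | 7 (58.3%) |
| 24 | 15 | 11 (73.3%) | 10 (66.7%) |

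**Step 5: primary endpoint.** A TEAE starts at or after first IMP and is followed to final follow-up. Neither the run-in boundary nor the treatment column changes that overall count.

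**The case against.** **The Day -1 cut may be deliberate.** It matches the six-day run-in and enrolment at Day -1, and SAP 5.5.1 already reports buprenorphine exposure separately for run-in and Days 1-2. The SAP also supersedes the protocol's statistical considerations. This is a fair defence of the choice, but not of leaving it out of the visible Appendix 2 rows. Nor does precedence over the protocol resolve the conflict between SAP 5.5.2 and 6.6.5. Part of Appendix 2 may be missing from the public text, so its completeness cannot be judged.

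**Little is lost in practice.** Day 1-2 events with a recorded start are still summarized for the Run-In Safety Population, and every event is listed with its onset. Subjects are resident in the clinic, so missing start times should be rare. A medication that misses the summaries is still listed under protocol 14.1. All this stands and limits the consequence. The protocol-SAP difference, however, needs no missing data to arise.

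**The open-ended assignment is an inference.** The SAP names the inputs without saying that an event stays with the last treatment indefinitely, and the table shells are in a separate document. This also stands: a post-treatment column might exist there. Keeping follow-up events in the overall count agrees with protocol 14.7.1, but that section does not say which treatment column they belong in.

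**Early stopping is partly handled.** Protocol 6.6 treats permanent study-drug discontinuation as withdrawal, and SAP 5.3.2 ends AE collection at early discontinuation except to resolve ongoing events. For a subject who stops during Days 3-9 this shortens the interval to the early termination visit. It does not remove it, and events in it would fall to INDV-2000+SUBOXONE.

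**Days are not events.** AE assessments are scheduled daily to Day 13 and then at Day 21. The day shares describe the window and do not estimate how many records would be misassigned.

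**Conclusion.** Both points hold. The run-in class has two end points across the documents, and SAP 5.5.2 and 6.6.5 disagree within the SAP. The disputed interval is Days 1-2, 25% of the SUBOXONE-alone dosing days. SAP 5.5.2 also states no end for the last treatment period: read as written, 8 of the 12 days from Day 10 to a Day 21 EOS follow the last dosing day (5 of 9 to 11 of 15 across the visit window), and 7 of 12 follow Day 14 (4 of 9 to 10 of 15).

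These figures are calendar counts for a subject who follows the schedule; no event rate is assumed. The second point rests on the SAP text without sight of the table shells. Overall TEAE incidence is unaffected. With at most 16 subjects, a few reassigned events could visibly change a by-treatment column, so the wording should be settled before the tables are produced.

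**What to change.** **Run-in end.** Use one definition in SAP 5.1.5, 5.5.2 and 6.6.5. There are two workable options:

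- Match protocol 10.1.1: first SUBOXONE film up to first INDV-2000 dose, with Days 1-2 shown as a sub-period.
- Keep the Day -1 cut, apply it in 6.6.5 as well, and list the departure in Appendix 2.

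Either way, 6.6.5 should assign events that began before first IMP and ended after it. Make the same choice for medications in 5.6.3 and 6.6.6 against protocol 9.6. If the Day -1 cut stays, name the population in which Day 1-2 medications of subjects without INDV-2000 are summarized.

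**Treatment end.** In SAP 5.5.2, close the INDV-2000-alone period at a stated point of the sponsor's choosing, say how events after early stopping are assigned, and report later events to EOS in a separate post-treatment column. Keep All Subjects running from first IMP to EOS for the primary endpoint. Use the same period ends in 5.6.3.

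**Cost.** SAP wording and table shells only, with no new data. The price is one more column and a cut-off that has to be justified.

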### **5.5.3. Additional Safety Assessments**

#### **5.5.3.1. Laboratory Data**

Planned laboratory evaluations ([Table 5](#)) will be summarized by analysis visit as observed values and, for numeric values, changes from baseline. Normal/abnormal shifts from baseline will also be summarized. Abnormal laboratory evaluations will be listed separately.

Laboratory evaluations done only at screening and during run-in will be listed but not summarized, unless included as baseline observation. Reported values of clinical laboratory parameters that include qualifiers (ie,  $<$ ,  $\leq$ ,  $>$ ,  $\geq$ ) will be listed as reported but will be summarized without the qualifier.

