- 28. Has total bilirubin $\ge 1.5 \times$ upper limit of normal (ULN) (with direct bilirubin >1.3 mg/dL), alanine aminotransferase (ALT) $\ge 3 \times$ ULN, aspartate aminotransferase (AST) $\ge 3 \times$ ULN, serum creatinine >2 × ULN, or international normalized ratio (INR) >1.5 × ULN at Screening).
- 29. Received medication-assisted treatment for OUD (e.g., methadone, buprenorphine) in the 30 days prior to providing written informed consent.
- 30. Received any prior treatment with a buprenorphine implant or injection.
- 31. Treatment for OUD required by court order.

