6.5.1.3 Part III - Individual Stopping Criteria

A subject will be discontinued if any of the criteria listed below are fulfilled:

AEs:

• The subject experiences an SAE that is not clearly unrelated to the IMP.

Laboratory Abnormalities:

The subject has an abnormality of one or both of the following parameters, whose temporal relationship to the IMP makes causality feasible, confirmed on repeat testing:

Confidential Page 36 of 108

- Serum ALT or AST >5 times the ULN or 2-fold above baseline if baseline is \geq 1.5 times ULN.
- Total serum bilirubin >2 times the ULN (>35% direct bilirubin).

ECG Criteria:

The subject fulfils the following ECG criteria based on the mean of triplicate measures (≥ 1 minute apart), completed once the first ECG demonstrates a prolonged interval:

• QTcF \ge 500 msec or uncorrected QT interval of >600 msec.

If the preceding criteria are met, the DRSC will conduct a review of the affected individuals to determine if any additional safety monitoring or changes to the protocol are required.

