### **5.1.4. General Analysis Conventions**

Categorical variables will be summarized using frequencies and percentages. Percentages will be reported to one decimal place.

Continuous variables will be summarized using descriptive statistics (e.g., n, mean, standard deviation (SD), distribution percentiles, range). The number of decimal places for minimums and maximums will be the same as the source data. The number of decimal places for means, medians, and interquartile ranges will be the same as the source data plus one, and the number of decimal places for measures of variance will be the same as the source data plus two. See [Section 6.5 \(Appendix 5\)](#) for summary statistics and precision specifications for PK data.

Data with qualifiers (e.g., “<”) will be listed with but summarized without the qualifier.

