### 5.5.3.3. Electrocardiogram (ECG) Data

Numeric 12-lead ECG parameters [heart rate, PR interval, QRS duration, QT interval, Fridericia's corrected QT interval (QTcF)] will be summarized as observed values and changes from baseline by analysis visit and time point. ECG interpretation (normal, abnormal not clinically significant, abnormal clinically significant) will be summarized by visit and time point as shifts from baseline.

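### Normal/abnormal laboratory shifts cannot show worsening in Part III subjects whose liver tests are already raised at baseline, and no visible table counts subjects by the protocol's own liver and QT limits

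*SAP*

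**What the plan says.** **Laboratory data.** SAP 5.5.3.1 plans observed values and changes by analysis visit, then: "Normal/abnormal shifts from baseline will also be summarized". Protocol 14.9.2 plans the same. The SAP adds that "Abnormal laboratory evaluations will be listed separately". SAP 5.1.4 gives the statistics for continuous variables, which include "distribution percentiles, range" as well as the mean and SD.

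**ECG.** Under SAP 5.5.3.3 the numeric parameters, QTcF among them, "will be summarized as observed values and changes from baseline by analysis visit and time point". The three-level interpretation "will be summarized by visit and time point as shifts from baseline". No QTcF or QT category is stated.

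**Who can enter Part III.** Exclusion 28 in protocol 5.3 removes subjects with "alanine aminotransferase (ALT) $\ge 3 \times$ ULN" and applies the same limit to AST, both at Screening. Values between 1 and just under 3×ULN are therefore allowed.

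**Limits the protocol acts on.** Protocol 6.5.1.3 stops a Part III subject at "Serum ALT or AST >5 times the ULN or 2-fold above baseline if baseline is" at least 1.5×ULN, at total bilirubin above 2×ULN with more than 35% direct, or at QTcF of 500 msec or more or uncorrected QT above 600 msec. Protocol 6.5.1.4 uses 3×ULN for ALT or AST, or the same two-fold clause, together with the bilirubin limit in two subjects.

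**Which values are used.** Baseline is the last value before first IMP, unscheduled and repeat values included (SAP 5.1.5). After baseline, SAP Appendix 3 uses CRF visits and takes the latest non-missing assessment when a visit has several.

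**The concern.** The Part III entry and stopping criteria are written for people who may start with raised liver tests. The shift table is written for people who start normal. The two-fold clause covers only subjects at or above 1.5×ULN, and all of them are already abnormal at baseline. So nobody who meets that clause can appear in the shift table as worsening, however many such subjects enrol.

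The same table treats a rise to just above normal and a rise past 5×ULN alike when the baseline is normal. It also does not separate low from high.

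Part III's primary objective is safety and tolerability, and SAP section 2 says all statistics are descriptive. The tables are therefore the result. A reader who wants to know how many subjects passed each limit would have to build that count from the listings.

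**Working it through.** The plan states no figure here to reproduce. The check classifies illustrative ALT pairs by the SAP's shift and by protocol 6.5.1.3.

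**Inputs.** Part III has up to 16 subjects (protocol 14.2). Abnormal high is taken as above 1×ULN. Two-fold above baseline is read as more than twice baseline. The ALT and QTcF pairs are assumptions; the raised ALT baselines lie inside the range that exclusion 28 allows.

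**Formula.** One subject moves the mean change by (post − baseline)/16.

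| ALT, ×ULN | SAP shift | Part III individual ALT/AST limit | Effect on mean change, ×ULN |
|---|---|---|---|
| 0.8 → 1.2 | normal → abnormal | not crossed | 0.4/16 = 0.025 |
| 1.2 → 5.5 | none | crossed (>5) | 4.3/16 = 0.269 |
| 1.5 → 3.1 | none | crossed (3.1 > 2 × 1.5 = 3.0) | 1.6/16 = 0.100 |
| 2.0 → 4.2 | none | crossed (4.2 > 2 × 2.0 = 4.0) | 2.2/16 = 0.138 |
| 2.5 → 4.9 | none | not crossed (<5; 4.9/2.5 = 1.96-fold) | 2.4/16 = 0.150 |
| 2.9 → 5.5 | none | crossed (>5) | 2.6/16 = 0.163 |

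The only pair that registers as a shift is the trivial one.

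**QTcF.** One subject rising from 440 to 505 msec moves the mean change by 65/16 = 4.1 msec. The reported maximum would show that value, but not how many subjects crossed a limit.

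**Repeat values.** The stopping limits need repeat laboratory testing or the mean of triplicate ECGs. If the repeat is recorded under the same visit, Appendix 3 keeps the later value, so a higher first value drops out of the mean, the range and the shift. Read literally, it would also keep the last of three tracings and not their mean.

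**What the adverse event tables capture.**
- A laboratory change that forces dosing to stop is a reportable AE (protocol 10.1.4). TEAEs leading to IMP discontinuation are counted (SAP 5.5.2).
- A potential Hy's Law case is an SAE by definition (protocol section 11) and enters the TESAE count.
- With ALT at or above 3 and below 5×ULN, bilirubin below 2×ULN and no hepatitis symptoms or rash, treatment may continue (protocol Appendix 4). Whether this becomes an AE depends on how the investigator applies protocol 10.1.4.
- Toxicity grading is not required in Part III (SAP 5.5.2), so grades do not fill the gap.

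**What a count would convey.** With 0 of 16, the one-sided 95% upper bound is 1 − 0.05^(1/16) = 17.1%. With 1 of 16 the estimate is 6.3% (exact 95% CI 0.2% to 30.2%).

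**The case against.** The strongest reply is that little is hidden. With at most 16 open-label subjects, every abnormal value is in a listing, and change from baseline, percentiles and range are reported by visit. Confirmed crossings that end dosing, and potential Hy's Law cases, reach the primary endpoint tables as TEAEs or TESAEs. All of this stands, and it makes the point one of presentation.

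Three stronger readings are tempting, and the documents do not support them.

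- A reader might infer that the report will hold no count of subjects who cross the limits. The AE route above counts many of them, as events and not by limit.
- A reader might infer that a set share of subjects, such as 4 of 16, cannot register liver worsening. The documents do not say how many will be abnormal at baseline. Baseline is the last value before IMP, scheduled on Day 3 after run-in and two further days of SUBOXONE, and not the Screening or admission value. Worsening also shows in the other outputs, and a raised baseline can still shift to normal.
- A reader might infer that unscheduled confirmatory samples never reach a post-baseline summary. Appendix 3 does not say so: a repeat recorded under a CRF visit becomes the value used. Samples outside a named visit are simply not addressed.

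Nor is it proven that no such table exists. SAP 6.4.3.1, under Safety Endpoints, is redacted, and the table mock-ups are in a separate document (SAP 5.1.3).

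**Conclusion.** The point holds in a limited form. The stated laboratory shift cannot show worsening in a subject who is still abnormal at the last pre-IMP value, including anyone who meets the protocol's two-fold clause. No visible text tabulates subjects by the ALT, AST, bilirubin, QTcF or QT limits. The same-visit rule can also remove a higher first value from the summaries.

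The real gap is mainly crossings that do not force discontinuation and are not judged clinically significant, such as ALT of 3 to <5×ULN under Appendix 4. These are listed but not tabulated. The number affected is unknown; each such subject is 1/16 = 6.25% of a full Part III group.

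This is a cheap improvement to the reporting and does not put the primary endpoint in doubt. It rests on the visible text, on normal meaning no more than 1×ULN, and on the redacted section and table shells not already supplying the count.

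**What to change.** If the redacted section or the table shells already contain a threshold table, cite it in SAP 5.5.3.1 and 5.5.3.3. Otherwise:

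1. **Liver bands, SAP 5.5.3.1.** Tabulate baseline against worst post-baseline value, using scheduled, unscheduled and repeat results. Bands: ALT and AST ≤1, >1–3, >3–5 and >5×ULN; total bilirubin ≤1, >1–2 and >2×ULN.
2. **Liver limits, SAP 5.5.3.1.** Count subjects against the limits already in the protocol: ALT or AST above 3× and above 5×ULN; two-fold above baseline where baseline is at least 1.5×ULN; bilirubin above 2×ULN with more than 35% direct. The two-fold count is needed in its own right, because 2.0 → 4.2 (crosses) and 2.5 → 4.9 (does not) fall in the same band cell. Footnote that this is a count of values: the stopping criteria also need repeat confirmation and a plausible time relation.
3. **Other numeric analytes.** Use low/normal/high shifts.
4. **ECG, SAP 5.5.3.3.** Count subjects by maximum post-baseline QTcF against the protocol's 450 (male), 470 (female) and 500 msec limits, and by uncorrected QT above 600 msec. Use the triplicate mean where triplicates were taken. Changes above 30 and 60 msec may be added, but those cut-offs are not in the documents.

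The cost is SAP wording and two further tables with small cells, from data already collected. No clinical rule changes.
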